All participants will complete the website questionnaires in order to standardize collection of our functional outcomes. Practitioners in both arms will not have access to the responses to the patient satisfaction questionnaires (WAI-SR and CSQ-8). The other questionnaire responses of the participants randomized to REVAMP management will be available to the practitioners performing the phone clinic evaluations. Enrolled subjects assigned to the in-person arm will only have access to the website's questionnaires but none of its other features. They will be informed that a research staff member will contact them to schedule their first clinic appointment. None of the questionnaires they complete on the website will be shared with their practitioners. At the time of their in-person clinic visits, these participants will complete the questionnaires that are routinely used as a part of the clinical site's usual care. That information will not be collected for analysis.

**Table 2.** Data collection and action schedule for all participants

Measures & Procedures	Baseline assessment	Initial clinical assessment	AutoCPAP set-up	1-week phone FU	1-month FU assessment	3-month FU assessment
	Week 0	Week 2-4	Week 8	Week 9-12	Week 12	Week 20
Eligibility criteria	In-person					
Informed consent	In-person					
Patient characteristic questionnaire	website					
Functional & QOL questionnaires†	website				website	Website Δ
Therapy process indicators‡		website		website	website	Website Δ
Clinical assessment*		In-person vs phone		Phone	In-person vs phone	In-person vs phone
APAP set-up			DME			
APAP adherence*				Wireless	Wireless	Wireless

DME = home health care company; FU=follow-up; QO =quality of life; Δ=performed every 3 months thereafter to the end of data collection

\* Subjects randomized to in-person management will have in-person clinic evaluations in the sleep center and subjects randomized to REVAMP management will have phone clinic sessions. APAP adherence in both groups will be obtained by wireless modem.

[figure not shown]
† Functional & QOL questionnaires: FOSQ-10, ESS, SF-12, CES-D, and EQ-5D; ‡ Therapy process indicators: WAI, CSQ-8 (performed within 1-week following each encounter)

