Following the first week of PAP treatment, a therapist with at least one year of experience managing patients with OSA will phone the participant. Using a standardized protocol, the therapist will evaluate the participant's response to treatment, inquire if any barriers are limiting PAP use, and provide advice on how to overcome those problems (see *Appendix 4*). The therapist will encourage the participant to review his/her PAP data on the website. The participant will be scheduled for 1- and 3-month follow-up phone calls with the therapist. Additional phone calls are allowed as clinically indicated and will be tracked. The therapist will have the option of consulting with the sleep specialist (MD or NP). Upon consultation, if it is felt that the problem cannot be addressed by phone, the participant will be scheduled for an in-person clinic appointment with the physician. The type, number

and duration of all encounters will be recorded in case report forms. All phone clinic sessions and other patient encounters will be documented in the participant's electronic medical record.

REVAMP has a secure message system that sends e-mail and text messages to the participant alerting him/her to login to the website to view a message. The REVAMP website will use this feature to remind the participant to complete questionnaires, view their PAP data, and keep scheduled phone clinic appointments.

*In-person management.* Participants in the in-person arm will be scheduled to meet with the sleep therapist for in-person set-up instructions for HST. Following HST, a sleep specialist (MD or NP) will conduct the initial in-person clinic evaluation. Participants diagnosed with OSA (using the same criteria detailed above for the REVAMP pathway) who are willing to start PAP treatment will be prescribed APAP. Sleep therapists with at least one year of experience managing patients with OSA will perform the follow-up clinic evaluations. Participants will receive a 1-week phone call and be scheduled for 1- and 3-month in-person follow-up clinic visits. Additional phone calls and clinic visits will be allowed as clinically indicated. The type, number and duration of all encounters will be monitored and documented in the participant's electronic medical record.

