**Analysis of secondary clinical outcomes in Aim 1.** Secondary outcomes in Aim 1 include changes from baseline to Month 3 in scores of the ESS, SF-12 (physical and mental health components), and CES-D questionnaires. For each secondary outcome, analogous analyses of covariance models will be used to determine least squares adjusted treatment group differences in mean change along with 95% confidence

intervals since non-inferiority deltas are not pre-specified. Baseline values of the outcome measures will be included in their respective ANCOVA models. The above results will be interpreted as hypothesis generating.

**Missing data methods.** The mixed model approach uses information in the covariance matrix of predictors and outcomes over time to implicitly impute missing 3-month FOSQ values. Of note, participants will complete the assessment battery at 1-month following initiation of treatment. Therefore, subjects missing month 3 results will not be excluded. These imputations are valid if the likelihood of missingness is independent of treatment group, conditional on observed data included in the model, i.e., if missing data are missing at random (MAR). For comparison with earlier studies, we will also perform the analyses using the last observation carried forward method. Finally, in sensitivity analyses, we will evaluate the impact of departure from the assumed MAR mechanism by using multiple imputation (MI) to implement a selection model approach. In this way, we will be able to compare estimated effects based on different assumptions about the missingness mechanism, and to assess the sensitivity of our estimates to these assumptions. If data on predictors is incomplete, we will use multiple imputation methods (as implemented in SAS PROC MI and MIANALYZE) to generate multiple imputed complete datasets, perform analyses, and then combine analysis results to produce estimates that are asymptotically unbiased, with standard errors that account for imputation uncertainty.

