**Modified intent-to-treat and per-protocol populations.** Primary analysis for non-inferiority will be based on all randomized participants initiated on APAP with at least one FOSQ follow-up score. In a secondary analysis, the non-inferiority test will be repeated using a per protocol cohort (patients who have been initiated on APAP and have non-missing endpoints at month 3), since protocol violations can add noise making it more difficult to distinguish between the two active treatment groups.

**Statistical methods for Aim 2.** Aim 2 will determine if REVAMP management of patients with OSA is cost-effective compared with in-person care. The perspective of the analysis will be that of the VA. While the VA has the general well-being of veterans as its goal, we will focus our attention on health care costs, in part because VHA patients with OSA are older and less likely to work. The analyses for Aim 2 will be based on all randomized participants, as this is the target population for the evaluation of Aim 2 and Aim 3 outcomes related to management of this patient population. We will perform a secondary analysis using the modified intention to treat sample (Aim 1 analysis set). The primary outcome measure in Aim 2 will be the difference in sleep-related cost between the two delivery modalities. Our hypothesis is 2a)  $H_0: \Delta C = 0$  vs  $H_A: \Delta C < 0$ . Based on data from our prior study of home vs in-lab diagnosis, we assume average 3-month sleep-related costs of \$1755 (SD, 745) for the home group and of \$2538 (SD, 1065) for the in-lab group. Resulting power is 1.0 for sample size of 114 per group and remains greater than 0.9 if, when including participants without OSA on HST and participants with CSA/CSR, the means are reduced by 25% and the SDs are increased by 25%.

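### Automated questionnaire reminders are described for the REVAMP arm only, so the self-completed FOSQ-10 would, as written, be collected with unequal prompting by arm

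*Combined protocol and SAP*

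**What the plan says.** The Aim 1 methods make the website the common source of patient-reported outcomes: "All participants will complete the website questionnaires in order to standardize collection of our functional outcomes". Table 2 lists the website as the only source of the functional and quality-of-life questionnaires, including the FOSQ-10, at the 1-month and 3-month assessments.

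The prompt appears once, in the text on the REVAMP pathway, where the secure e-mail and text system is introduced: "The REVAMP website will use this feature to remind the participant to complete questionnaires, view their PAP data, and keep scheduled phone clinic appointments".

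For the other arm the Aim 1 methods say: "Enrolled subjects assigned to the in-person arm will only have access to the website's questionnaires but none of its other features". The only staff contact described there concerns scheduling: "They will be informed that a research staff member will contact them to schedule their first clinic appointment". In-person participants also fill in their clinic's routine forms, but of these the plan says: "That information will not be collected for analysis". The In-person management paragraph mentions no questionnaire prompt.

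The Statistical Analysis section bases the primary non-inferiority analysis on "all randomized participants initiated on APAP with at least one FOSQ follow-up score". The per-protocol set requires non-missing month-3 endpoints. Under Missing data methods the plan states: "These imputations are valid if the likelihood of missingness is independent of treatment group". That sentence goes on to make the condition hold given the observed data in the model, that is, missing at random (MAR).

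**The concern.** A questionnaire reminder affects who returns the form and when. If one arm has automated prompts and the other has none described, completion rate and completion day may differ by arm because of a procedure that the trial controls.

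This matters more than usual here because returning a form decides entry to the analysis sets. A participant on APAP who completes no follow-up FOSQ leaves the primary set, and one without month-3 endpoints leaves the per-protocol set. The per-protocol analysis is therefore not an independent check on this problem. The clinic's own forms cannot replace a missed FOSQ-10, and in-person practitioners do not see the website responses, so a visit would not necessarily reveal a missed form.

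The SF-12 and EQ-5D (which supply the Aim 2 preference scores) and the WAI-SR and CSQ-8 (Aim 3) come through the same website and share the exposure. APAP adherence, the other primary hypothesis, arrives by wireless modem in both arms and does not.

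**Working it through.** **1. The text, side by side.**

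| Item | REVAMP | In-person |
|---|---|---|
| Where FOSQ-10 is completed | Website | Website |
| Automated questionnaire reminder | Described | None described; website features other than the questionnaires excluded |
| Other prompt to complete the forms | 1-week, 1- and 3-month calls, not stated to cover the forms | 1-week call and 1- and 3-month visits, not stated to cover the forms |
| Other reason to log in | Daily review of PAP data | None described |
| FOSQ-10 completion window | None stated | None stated |

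Table 2 gives the WAI and CSQ-8 a one-week window after each encounter but gives the FOSQ-10 none.

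**2. The plan's own figures.** Inputs from Sample size, and power: SD 2.80, margin 1, 85% power; one-sided α 0.05 from the non-inferiority methods. Normal approximation: n = 2 × 2.80² × (1.645 + 1.036)² / 1² ≈ 113 per group. The noncentral t gives power 0.849 at 113 and 0.852 at 114, so 114 is reproduced. Enrolment: 228 / (0.8 × 0.8) = 356.25, which matches 356. The 20% drop-out is not split by arm, and the plan gives no completion rate by arm. Everything below therefore rests on assumed rates.

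**3. Illustration A: shift in raw observed means.** Under a normal selection model, observed mean minus full mean = ρ × SD × φ(z_p)/p, where p is the completion rate and ρ the correlation between tendency to respond and FOSQ-10 change.

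- p = 0.90: 0.1755/0.90 = 0.195
- p = 0.85: 0.2332/0.85 = 0.274
- p = 0.75: 0.3178/0.75 = 0.424
- 90% v 75%: (0.424 − 0.195) × 2.80 = 0.64; × 0.3 = 0.19, × 0.5 = 0.32
- 85% v 75%: (0.424 − 0.274) × 2.80 ≈ 0.42; × 0.3 = 0.13, × 0.5 = 0.21

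With the lower rate in the in-person arm, the shift goes against REVAMP if those with better change respond more readily, and in its favor if they respond less readily.

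**4. Illustration B: complete-case comparison.** Participants starting APAP per arm: 356 × 0.8 / 2 = 142.4. If non-completers' mean change is g points below completers', the REVAMP-minus-in-person estimate shifts by (d_R − d_P) × g, where d is the missing fraction. SE = 2.80 × √(1/n_R + 1/n_P).

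- Equal missingness, 20%/20%: 113.9 v 113.9 observed, power 0.853.
- Unequal, 10%/30%: 128.2 v 99.7 observed, SE 0.374. Power is 0.848 with no completer gap, so unequal numbers alone cost little.
- 10%/30% with g = 1 or 2: (0.10 − 0.30) × g = −0.20 or −0.40; power 0.69 or 0.48.
- 10%/30% with non-completers better by 1 or 2: +0.20 or +0.40; one-sided type I error rises from 0.05 to 0.13 or 0.28.

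Both illustrations describe unadjusted comparisons, not the planned mixed model.

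**The case against.** **Nothing forbids reminders in the in-person arm.** A reader might infer that they are switched off by rule. No sentence says so. The restriction concerns access to website features, while the reminder is a message sent out, and staff could prompt participants in ways not described. This stands: the gap comes from reading two places together. If staff are meant to prompt, the protocol should say so.

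**Unequal missingness does not breach the missing-data assumption.** A reader might take the stated condition to fail once completion differs by arm. It does not. The condition is conditional on observed data, and arm is in the model. Bias also needs missingness to depend on outcome after allowing for arm, baseline and 1-month FOSQ. This stands.

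**Net effort is not known to be lower in person.** Clinic visits at months 1 and 3 coincide with the FOSQ-10 and may act as cues, and REVAMP participants carry the extra task of daily website review. This stands against any claim about net burden. It does not supply a described prompt.

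**The reminder is partly care.** REVAMP responses, apart from the WAI-SR and CSQ-8, are available to the practitioners running phone sessions, so completing the forms feeds management. This is correct. But the same forms supply the primary endpoint in both arms, and prompting in-person participants would not pass their answers to their practitioners.

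**The analysis already responds.** The mixed model uses 1-month scores, and last observation carried forward and a multiple-imputation selection model are planned. A missed month-3 form alone does not remove anyone from the primary set. All true, but none of this equalizes collection, and a participant with no follow-up FOSQ stays outside that set.

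**Conclusion.** The plan as written prompts one arm for the self-completed primary endpoint and describes no prompt for the other, contrary to its own aim of standardized collection. That is an avoidable risk to the FOSQ-10 non-inferiority comparison.

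It is not a demonstrated error. The documents do not show that completion will differ, in which direction any bias would run, or how large it would be. The shifts of 0.13 to 0.32 points in Illustration A depend on assumed completion rates (90% or 85% v 75%) and assumed correlations (0.3 to 0.5), and they apply to raw means. A reader might take them as the expected bias of the trial; they show only that a plausible imbalance could use a noticeable part of the 1-point margin. The mixed model would remove whatever part arm, baseline and 1-month data explain.

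The point is a cheap improvement, best made before follow-up data are collected because uncollected scores cannot be recovered.

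**What to change.** In the Aim 1 methods, where website access by arm is described, and in the REVAMP pathway text, state one questionnaire-reminder procedure for both arms: same channel, wording, timing, number of repeats and completion window around the 1-month and 3-month assessments. Applying it to the later 3-monthly questionnaires as well would cover the Aim 2 preference measures. Keep the messages about PAP data and phone appointments as REVAMP-only features.

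Report FOSQ-10 completion rate and completion day by arm at months 1 and 3, so that any remaining imbalance can be seen.

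The cost is a configuration change to an existing message system and a wording change in the protocol. Sample size, margin and analysis model stay as they are. The small downside is that in-person participants receive a few automated messages that usual care would not send.

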## OUTCOME MEASURES

### Aim 1 – Outcome Measures (see Appendix 3 for validated questionnaires)

Subject Characteristics Questionnaire is a 15-min self-administered and provides the following information: sleep-related complaints, history of risk factors for sleepiness, past medical history, education level, employment status, current medication use, and an assessment of health literacy.

Functional Outcomes of Sleep Questionnaire (FOSQ-10). The FOSQ-10, a disease-specific questionnaire and our primary outcome measure, will be used to compare functional benefit from APAP treatment. The 10-question instrument has been used in research and clinical practice to measure the impact of daytime sleepiness on activities of daily living. FOSQ-10 has an internal consistency of  $\alpha = 0.87$  and a pre-treatment correlation with the total FOSQ (36 questions) of  $r = 0.96$ . After 3 months of CPAP treatment the correlation was  $r = 0.97$ . Effect sizes with treatment for both instruments were highly correlated and indicate ability to measure meaningful change. Differences were observed between FOSQ-10 scores for normal controls and OSA patients. The measure is at a 5th grade reading level and takes less than 5 min to complete.

APAP adherence will be objectively monitored by exporting the data from the REVAMP website. Average hours per day of APAP use over the initial 3 months of treatment will be used to test our hypothesis that participants who receive telemedicine-based versus in-person care have similar APAP adherence. In addition to adherence data, the APAP units provide information on treatment efficacy.

Epworth Sleepiness Scale Questionnaire (ESS) assesses perceived daytime sleepiness and will be used to test our hypothesis that participants in the two arms have similar improvements in subjective daytime sleepiness (change in person level disability) on PAP therapy. The respondent rates the likelihood of falling asleep in eight soporific situations using a 4-point Likert scale ranging from “never dozing” to “high chance of dozing”. Multiple RCTs report a reduction in ESS with PAP therapy in OSA patients.

Medical Outcomes Study Short Form-12 (SF-12) is a 12-item self-administered health-related quality of life questionnaire, with established reliability and validity, providing summary information on physical and mental health status. The physical and mental health scores will be used to compare overall functional benefit between the two interventions. SF-12 uses a Likert scale of 1-3 for physical function; 1-5 for bodily pain, social function, and general health perceptions; 1-6 for vitality and mental health; and a dichotomous scale of yes/no for the presence of role function limitations. The higher the score, the higher the level of health or functioning. SF-12 is widely used to assess health-related quality of life in many populations, including OSA.

Center for Epidemiological Studies Depression Scale (CES-D) is a 20-item standard instrument devised using items from 5 validated depression scales. Likert-style responses for each symptom indicates how often in the past week the subject has experienced the symptom. Scores range from 0 (not at all to 1 day in the week for all 20 symptoms) to 60 (5 to 7 days in the week for all 20 symptoms). The internal consistency of the measure (Cronbach alpha value) ranges from 0.83 to 0.90.

### Aim 2 - Measures to be used in cost, utility, and cost-effective analysis (see Appendix 3 for questionnaires)

Medical service use and costs, stratified by whether or not they are related to the diagnosis and treatment of OSA, will be collected for the 6 months prior to enrollment and the entire observation period following enrollment. We will track the cost of all tests, treatments, and equipment (for diagnosis, PAP). Starting in the third quarter of the study (equivalent to the beginning of the second quarter of enrollment) and continuing quarterly for a total of 6 quarters, providers will be asked in the second week of the quarter to report the time they spent managing individual participants during the prior week. Obtaining measurements for a week reduces problems of recall; obtaining them over a year allows capture of changes in physician time that may occur over the study period. The cost of participant travel time will be based on the distance the participant lives from the sleep center. Participants will be asked to recall the time they spent performing activities related to sleep services during their one- and three-month follow-up interviews. We will also collect all costs pertaining to non-OSA sleep-related disorders.

Medical service use and cost data incurred within the VHA will be obtained through access to the Managerial Cost Accounting (MCA) System at the Corporate Data Warehouse (CDW), the VA national data repository. MCA National Data Extracts (NDEs) data originate from various site-level MCA databases and subsystems at the patient level. We will select NDEs to obtain in-patient, outpatient, laboratory, pharmacy, radiology, and surgery services provided to each participant and their associated cost. To gain research access to MCA data, a Data Access Request Tracker (DART) application will be submitted to the National Data Systems (NDS). Once approved for access, the requested information, typically in the format of SQL server output tables, will be provided by the VA Informatics and Computing Infrastructure (VINCI). Fee-based non-VA care on the CDW will be requested from VINCI. Cost and use of Centers for Medicare and Medicaid Services (CMS) by participants

who are CMS beneficiaries will be obtained by submitting a standard request to the VA Information Resource Center (VIREC) to access the VA/CMS repository data that is also available on the CDW. Non-VA and non-CMS services not captured by VA database inquiries will be derived from patient self-reported data collected on questionnaire. The latter service use will be costed out using data that will be derived from the cost data at the respective sites as well as Federal reimbursement schedules when that medical center's cost data are not available. Participants will be asked to provide details about any traffic accidents and we will cost them out using published data on the cost of such accidents. Costs of wireless PAP data transmission, when applicable, will be included in the analysis. [name], our database manager, has strong experience working in VINCI and with SQL server output tables to create SAS datasets.

Preference-weighted QOL. As recommended by the Panel on Cost-effectiveness in Health and Medicine, QALYs will be assessed using preference-weighted generic quality of life instruments. Preference-weighted health-related quality of life will be expressed in terms of the SF-6D (primary preference measure calculated by use of the SF-12 scoring algorithm), and the EQ-5D (secondary preference measure). We propose use of both the SF-6D and EQ-5D for secondary analyses of treatment differences because prior research has indicated that patients with OSA provide significantly different responses to these 2 instruments. While there is little information available for identifying which is a better measure of preference-weighted QOL, either in general or specifically for OSA and its treatment, Schmidlin et al. have recommended use of the SF-6D and the EuroQOL feeling thermometer for the evaluation of OSA treatments.

SF-6D will be used as the primary measure of patient preferences. SF-6D can be derived from the SF-12, which, in combination with data on survival, allows the calculation of QALYs. The SF-6D yields a preference-based single index measure for health from these data using general population values. It focuses on seven of the eight health domains covered by the SF-12: physical functioning, role participation (combined role-physical and role-emotional), social functioning, bodily pain, mental health, and vitality. Scoring of the SF-6D takes into consideration any limitations in the kind of work or other activities as the result of physical health; accomplishing less due to emotional problems; bodily pain and its interference with normal work; nervousness, depression, and energy level; and interference with social activities due to physical or emotional problems. Research has shown that a meaningful health state classification measure, the SF-6D, can be created by applying a scoring method developed by Brazier and colleagues.

EQ-5D will be used as a secondary measure of patient preferences. The self-report questionnaire includes the respondent's self-rated health status on a vertical graduated (1-100) visual analogue scale. In addition, a multi-attribute utility scale comprises 5 dimensions of health (mobility, self-care, usual activities, pain/discomfort, anxiety/depression) and produces a single index score for each state of health. Each dimension comprises 3 levels (no problems, some/moderate problems, extreme problems). A unique score is calculated for the EQ-5D, by applying a scoring method developed by Shaw and colleagues.

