The clinical sites will use a type 3 portable monitor that records nasal pressure, rib cage and abdominal movement, pulse oximetry, and body position. Two of the sites use the T3 monitor (Nox Medical) and the third site uses Nomad, Nihon Kohden. We will control for diagnostic bias by ensuring that the sites record identical channels, at an identical sampling frequency. The monitor will be distributed to participants in the REVAMP arm without in-person set-up instructions, and they will be directed to the REVAMP website to review a video on OSA and PAP treatment developed by the American Sleep Apnea Association and a step-by-step instructional video and brochure explaining HST set-up (Appendix 2). Postal materials will be provided to mail the monitor back to the sleep center using a carrier that allows tracking of the package. Participants randomized to in-person management will be scheduled to meet with a technologist at the sleep center to receive in-person instructions on how to perform the test. During the visit, the subject will be shown the videos and provided with the set-up brochure (Appendix 2). The therapist will explain how to operate the monitor, demonstrate placement of the sensors, and answer the participant's questions. The patient will be given the option of returning the monitor by mail or in-person. Participants in both arms will be provided a 24/7 phone number to contact an on-call PSG technologist at the site's sleep center with any questions about the set-up.

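### The Aim 2 cost list has no item for the running cost of REVAMP, so the saving tested in hypothesis 2a would be overstated if costs are collected only as listed

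*Combined protocol and SAP*

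**What the plan says.** Under Statistical methods for Aim 2, the combined protocol and SAP states: "The primary outcome measure in Aim 2 will be the difference in sleep-related cost between the two delivery modalities". It also states: "The perspective of the analysis will be that of the VA". Hypothesis 2a takes a negative cost difference as its alternative. The analysis set is all randomized participants.

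The cost sources are itemized in the Aim 2 measures section:

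- Tests and equipment: "We will track the cost of all tests, treatments, and equipment (for diagnosis, PAP").
- VHA services: "We will select NDEs to obtain in-patient, outpatient, laboratory, pharmacy, radiology, and surgery services provided to each participant and their associated cost".
- Fee-based and CMS care, self-reported outside care, and traffic accidents.
- Provider time, from a one-week report each quarter over six quarters, and participant travel and activity time.
- Data transmission: "Costs of wireless PAP data transmission, when applicable, will be included in the analysis".

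The REVAMP pathway uses resources of another kind. PAP data pass daily from the manufacturer's server to the website, which displays them to participants and practitioners. In addition, "REVAMP has a secure message system that sends e-mail and text messages to the participant". For the home sleep test (HST) in this arm, "Postal materials will be provided to mail the monitor back to the sleep center using a carrier that allows tracking of the package".

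**The concern.** The platform is what distinguishes the experimental arm. Its hosting, upkeep, support, data import and messaging are recurring costs shared across users, and they fall within a VA perspective. They are not patient-level inpatient, outpatient, laboratory, pharmacy, radiology or surgery services, so the listed extracts are not an evident source. Provider-time reports would not show them either. The in-person counterparts, set-up and clinic visits, do fall naturally under outpatient services and provider time.

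Wireless transmission does not fill the gap. Table 2 has adherence collected by modem in both arms, so that cost largely cancels in the difference.

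The effect would run in one direction, toward the alternative of hypothesis 2a. The same amount would enter the total cost difference and the numerator of the cost-effectiveness ratio. As a recurring cost, it would also accumulate over the full follow-up of up to two years.

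**Working it through.** **Inputs from Statistical methods for Aim 2.** The assumed three-month cost is $"1755 (SD, 745) for the home group", and $2,538 (SD $1,065) for the in-lab group. The assumed saving is therefore 2,538 − 1,755 = $783. The power statement uses 114 per group. The analysis set is all 356 randomized, which at 1:1 is 178 per arm.

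**Assumptions.** No alpha is stated for hypothesis 2a. I take 5% one-sided, following the one-sided alternative. The uncounted net REVAMP cost per participant, c, is not given anywhere; $50, $100 and $200 are illustrations.

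**Reproducing the plan's power.** SE = √[(SD₁² + SD₂²)/n], and power = Φ(difference/SE − 1.645).

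- Base case, n = 114: SE = √[(745² + 1,065²)/114] = $121.7. Power = Φ(783/121.7 − 1.645) = 1.000, against a stated 1.0.
- Means 25% lower and SDs 25% higher, n = 114: difference = 0.75 × 783 = $587.25 and SE = 1.25 × 121.7 = $152.2. Power = Φ(587.25/152.2 − 1.645) = 0.987, or 0.971 two-sided, against a stated value above 0.9.

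Both figures reproduce.

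**Bias.** If REVAMP cost is recorded as its true value minus c, the estimated REVAMP-minus-in-person difference is shifted by −c. The overstatement of the saving is c, dollar for dollar.

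**False saving if true costs are equal, n = 178.** SE = √[(745² + 1,065²)/178] = $97.4, so a saving is declared at about 1.645 × 97.4 = $160. With SDs 25% larger, SE = $121.8 and the threshold is about $200. The probability of a false saving is Φ(c/SE − 1.645).

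| Assumed c | SDs as planned | SDs 25% larger |
|---|---|---|
| $0 | 5% | 5% |
| $50 | 13% | 11% |
| $100 | 27% | 21% |
| $200 | 66% | 50% |

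**If the plan's assumed saving is what would be recorded with c left out.** The true saving is then 783 − c: $733, $683 or $583 for the three values of c. In the less favourable scenario it is 587.25 − c: about $537, $487 or $387. Erasing the saving altogether needs c = $783 or $587. In the less favourable scenario with 178 per arm and c = $200, a fully costed analysis would still declare a saving with probability Φ(387.25/121.8 − 1.645) = 0.94.

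**The case against.** The strongest reply is that silence is not exclusion. Nothing in the plan says platform costs will be left out, and the wireless sentence shows that technology costs outside the listed VHA service categories can be added. This stands to the extent that the result cannot be called biased already; it would be biased if the list is followed as written. It does not close the gap, because no listed item would collect these costs and no rule says how a shared cost becomes a cost per participant.

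A reader might also infer that mailing of the HST monitor is uncounted. The documents do not support that. The commitment to track all tests and equipment can reasonably cover delivery and return. The section on home sleep testing also lets in-person participants return the monitor by mail, so only a net difference could matter.

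Nor is every platform cost a REVAMP-arm care cost. In-person participants complete study questionnaires on the website, it performs the randomization, and adherence data are exported from it. Charging all of this to REVAMP would err in the other direction. The modem-to-manufacturer part of the data chain is arguably covered by the wireless item, which leaves the import to the website as the unnamed link.

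Finally, the error rates assume a true difference of exactly zero, and under the plan's own assumed saving a modest omission would not change the conclusion. That is correct arithmetic, but the $783 gives limited reassurance. It comes from a study of home versus in-laboratory diagnosis, whereas here both arms start with an HST and are prescribed APAP under the same criteria. Much of that contrast is absent, so the true saving could be considerably smaller.

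**Conclusion.** The concern holds in conditional form. The itemized sources contain nothing that would capture REVAMP's recurring operating and messaging cost. If followed as written, they overstate the saving in the primary Aim 2 outcome by the uncounted net cost per participant.

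The size cannot be determined from the documents. The false-saving probabilities illustrate what assumed unit costs would do when true costs are equal, given normal approximation, the plan's SDs and an assumed one-sided 5% test. They are not forecasts. An omission of $50 to $200 could decide hypothesis 2a if the true saving is small, but it would leave most of the saving the plan assumes. The documents do not support concluding that REVAMP's apparent saving would be an artefact of the cost list.

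**What to change.** Add to the Aim 2 measures section, after the sentence on wireless transmission, wording such as:

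> The recurring cost of delivering care through REVAMP (hosting, maintenance, technical support, import of PAP data to the website, e-mail and text messaging) will be counted as sleep-related cost in the REVAMP arm. Research-only functions (randomization, study questionnaires, data export) and one-off development cost are excluded. Shipping of HST monitors will be counted in whichever arm it occurs.

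Name the cost source and the per-participant allocation rule before analysis, since a rule for shared cost chosen afterwards could be shaped by the result. Report hypothesis 2a in a sensitivity analysis over a range of unit costs and user volumes, from trial volume to VA-wide volume. Which volume should drive the main result is open to argument, because spreading fixed hosting over trial participants alone may overstate the cost in routine use. The plan should make that choice explicitly.

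The cost is a few lines of SAP text and a request for running-cost and shipping records, with no new participant data. The estimated saving will be somewhat smaller.
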